## 9.2 Exploratory Objectives

Serology and cell mediated immunity objectives will be analyzed using the immunogenicity population. All exploratory endpoints will be assessed with two-sided tests and alpha set to 0.05.

### *Serology*

Microneutralization (MN), SARS-CoV-2 binding antibody and viral neutralization, and circulating virus objectives will all use the same statistical methods as the primary HAI objective. Waning objectives will use parametric models to estimate the rate of antibody decline by time since vaccination. Estimated GMTs and fold change will be presented for each time point with their associated 95% confidence intervals.

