Demographic and health data (including influenza and COVID-19 vaccination and infection history) will be collected upon enrollment and verified after enrollment via electronic medical record extraction. Enrolled participants will be randomized to one of the following interventions (2:1:1) using a permuted block method stratified by age group (aged 6-11 years and 18-64 years) and site: (i) concomitant administration of the mRNA COVID-19 vaccine (Moderna) and quadrivalent influenza vaccine (cclIV4); (ii) sequential administration of the quadrivalent influenza vaccine (cclIV4) at Visit 1 (day 0) and the mRNA COVID-19 vaccine (Moderna) at Visit 2 (day 28); (iii) sequential administration of the mRNA COVID-19 vaccine (Moderna) at Visit 1 (day 0) followed by the quadrivalent influenza vaccine (cclIV4) at Visit 2 (day 28). Whole blood samples to isolate sera, PBMC and plasma (target to collect PBMC and plasma samples at every visit from a subset of 250 participants; 200 adults and 50 children) will be collected prior to vaccination administration at Visit 1 (day 0) and Visit 2 (day 28). Participants will not be blinded to vaccine group and will receive two vaccines in separate limbs (for the concomitant vaccination [group i]) or one vaccine at Visit 1 (day 0) and a second vaccine at Visit 2 (day 28) (for sequential vaccination [groups ii and iii]) in an unblinded manner.

Participants will provide a blood sample for isolation of serum, PBMC, and plasma (target to collect PBMC and plasma samples at every visit from a subset of 250 participants; 200 adults and 50 children) at Visit 3 (day 56; post-vaccination 2) and Visit 4 (day 180; end of local flu circulation). If participants exhibit ARI during the study period, they may be asked to present for

an acute (<10 days after symptom onset) and convalescent (28 days after acute visit) visit to provide a nasal swab for viral testing (acute visit only) and blood sample for isolation of serum, PBMC, and plasma (acute and convalescent visit for those with positive viral molecular test for influenza or SARS-CoV-2). Influenza virus and SARS-CoV-2 serologic and cellular immunity testing will be conducted at CDC and/or a CDC-approved site.

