### 2.2 Exploratory

EO1: To determine baseline and post-vaccination influenza antibody titers by microneutralization (MN), in a subset of samples, against cclIV4 vaccine antigens following concomitant administration with mRNA vaccine or alone.

EO2: To determine baseline and post-vaccination SARS-CoV-2 antibody binding titers and ACE2 binding inhibition and viral neutralization, on a subset of specimens, against Moderna mRNA COVID-19 vaccine antigens following concomitant administration with cclIV4 or alone.

EO3: To determine duration and rate of waning of influenza HAI and MN antibody titers against cclIV4 vaccine antigens and circulating influenza viruses.

EO4: To determine duration of and rate of waning of SARS-CoV-2 antibody titers and viral neutralization titers, on a subset of samples, against Moderna mRNA COVID-19 vaccine antigens and circulating SARS-CoV-2 variants.

EO5: To determine influenza HAI and MN antibody titers against circulating influenza viruses during baseline and post-vaccination or post-infection.

EO6: To determine SARS-CoV-2 antibody binding titers and viral neutralization titers (in a subset of samples) against circulating SARS-CoV-2 variants during baseline and post-vaccination.

EO7: To compare the frequencies of antigen-specific T and B cells utilizing conventional ELISPOT assays, high-dimensional flow cytometric analysis of innate and adaptive immune cell

phenotype characterization using fluorochrome-conjugated antigen tags, and intracellular cytokine staining to 2023-24 cclIV4 and mRNA COVID-19 vaccines administered either concomitantly or sequentially, 28 days apart.

EO8: To compare transcriptome, B cell receptor (BCR) and T cell receptor (TCR) diversity of antigen-specific cells and assess serological antibody repertoire (clonotypes) using 10X genomics platform, and liquid chromatography/mass spectroscopy in a subset of participants.

EO9: To investigate the waning of antigen-specific B cells and antibody clonotypes in a subset of participants.

EO10: To describe safety of concomitant versus sequential administration of cclIV4 and mRNA COVID-19 vaccination.

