#### 3.2 Exploratory

EO1:

- I. Proportion of participants in each vaccination group with a seroprotective MN (in a subset of samples) titer ( $\geq 1:40$ ) pre- and post-cclIV4 immunization for each 2023-24 influenza vaccine antigen
- II. Proportion of participants in each vaccination group achieving MN (in a subset of samples) seroconversion (a titer  $\geq 1:40$  following cclIV4 if the baseline titer is  $< 1:10$  or a four-fold rise in titer if the baseline titer is  $> 1:10$ ) following cclIV4 vaccination for each 2023-24 influenza vaccine antigen
- III. HAI (in a subset of samples) MN for each 2023-24 influenza vaccine antigen pre- and post-cclIV4 in each vaccination group
- IV. GMFR in MN (in a subset of samples) titers for each 2023-24 influenza vaccine antigen in each vaccination group

EO2. GMT for SARS-CoV-2 binding antibody titer and viral neutralization titer (for a subset of samples) pre- and post-vaccination with mRNA COVID-19 vaccine

EO3:

- I. HAI and MN GMT for each 2023-24 influenza vaccine and circulating influenza virus antigens at visit 1, visit 2, visit 3, and visit 4 for each vaccination group
- II. Geometric mean fold change in HAI and MN titers for each vaccination group from visit 1 to visit 2, visit 3, and visit 4 for each 2023-24 influenza vaccine and circulating influenza virus antigen

EO4:

- I. SARS-CoV-2 binding antibody and viral neutralization GMT for each mRNA COVID-19 vaccine and circulating SARS-CoV-2 virus antigens at visit 1, visit 2, visit 3, and visit 4 for each vaccination group
- II. Geometric mean fold change in SARS-CoV-2 and viral neutralization (in a subset of samples) titers for each vaccination group from visit 1 to visit 2, visit 3, and visit 4 for each COVID-19 Moderna mRNA COVID-19 vaccine and circulating SARS-CoV-2 virus antigen

EO5

- I. Proportion of participants in each vaccination group with a seroprotective titer ( $\geq 1:40$ ) pre- and post-cclIV4 immunization (visits 1-3) and/or pre- and post-influenza infection (acute and convalescent visits), if applicable, for each 2023-24 circulating influenza virus antigen

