- II. Proportion of participants in each vaccination group achieving seroconversion (a titer  $\geq 1:40$  following cclIV4 if the baseline titer is  $< 1:10$  or a four-fold rise in titer if the baseline titer is  $> 1:10$ ) following cclIV4 vaccination (visit 1 to visits 2-3) and/or influenza infection (acute to convalescent visits), if applicable, for each 2023-24 circulating influenza virus antigen
- III. HAI and MN GMT for each 2023-24 circulating influenza virus antigen pre- and post-cclIV4 (visits 1-3) and/or pre- and post-influenza infection (acute and convalescent visits), if applicable, in each vaccination group
- IV. GMFR in HAI or MN titers for each vaccination group following cclIV4 vaccination (visit 1 to visits 2-3) and/or influenza infection (acute to convalescent visits), if applicable, for each 2023-24 circulating influenza virus antigen

EO6:

- I. SARS-CoV-2 binding antibody and viral neutralization (for a subset of samples) titers GMT at pre- and post-vaccination (visits 1-3) and/or pre- and post-SARS-CoV-2 infection (acute and convalescent visits), if applicable, against 2023-24 circulating SARS-CoV-2 virus antigens
- II. GMFR in SARS-CoV-2 binding antibody and viral neutralization (for a subset of samples) titers following mRNA COVID-19 vaccination (visit 1 to visits 2-3) and/or SARS-CoV-2 infection (acute to convalescent visits), if applicable, against 2023-24 circulating SARS-CoV-2 virus antigens

EO7:

- I. The frequency of antigen-specific T and B cells to influenza and SARS-CoV-2 at visit 1, visit 2, visit 3, visit 4, and acute and convalescent visits, if applicable
- II. High-dimensional flowcytometric analyses of innate and adaptive immune cells
- III. ELISPOT evaluation for SARS-CoV-2 memory B cells

EO8: BCR and TCR diversity and clonal dominance (antibody clonotypes) of serological repertoire in a subset of participants

EO9: The frequency of antigen-specific B cells and clonal dominance (antibody clonotypes) to influenza and SARS-CoV-2 at visit 1, visit 2, visit 3, visit 4, and acute and convalescent visits (if applicable) in a subset of participants

E10:

- I. Number and percent of participants reporting fever or injection site and/or systemic reactions during the first 3 days following each vaccination visit stratified by severity and, for those reporting symptoms, their impact on health

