## 6.4 SARS-CoV-2 Immunogenicity Population

The SARS-CoV-2 Immunogenicity Population is a subset of the mITT Population that includes only subjects who received both vaccines, provide visit 1 and visit 2 blood draws available with MSD results for analysis within the protocol-defined time frame, did not have an influenza or SARS-CoV-2 infection between visits 1 and 2, and had no protocol violations affecting immunogenicity. Protocol violations affecting the immunogenicity analyses are defined in the Statistical Analysis Plan (SAP) Appendix 1. The acceptable visit window for sample analysis will be +14 days from the target date. Should 10% or more of the total study population be excluded from the SARS-CoV-2 Immunogenicity Population due to missing the visit window, then an additional analysis will be performed including these subjects with the missing visit window exclusion.

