## 9 ANALYSIS OF STUDY OBJECTIVES

### 9.1 Primary Objective

The primary objective will be analyzed using the immunogenicity population. All endpoints will be assessed with two-sided tests and alpha set to 0.05.

*Endpoint i:*

The proportion of participants with a seroprotective HAI before and 28-42 days after immunization will be compared between group i (concomitant administration) and ii (influenza administered first), using the following null ( $H_0$ ) and alternative ( $H_1$ ) hypotheses:

$H_0$ : Simultaneous group – Sequential group = 0

$$H_0: \pi_1 - \pi_2 = 0$$

$$H_1: \pi_1 - \pi_2 \neq 0$$

where  $\pi$  is the seroprotective rate.

P values and confidence intervals for the geometric mean titer ratio will be estimated using a logistic regression adjusted for site.

*Endpoint ii:*

The proportion of participants achieving seroconversion will be compared between group i (concomitant administration) and ii (influenza administered first), using the following null ( $H_0$ ) and alternative ( $H_1$ ) hypotheses:

$H_0$ : Simultaneous group – Sequential group = 0

$$H_0: \pi_1 - \pi_2 = 0$$

$$H_1: \pi_1 - \pi_2 \neq 0$$

where  $\pi$  is the seroconversion rate.

P values and confidence intervals for the geometric mean titer ratio will be estimated using a logistic regression adjusted for site.

*Endpoint iii:*

GMTs before and 28-42 days after immunization will be compared between group i (concomitant administration) and ii (influenza administered first), using the following null ( $H_0$ ) and alternative ( $H_1$ ) hypotheses:

$$H_0: \mu_1 / \mu_2 = 1$$

$$H_1: \mu_1 / \mu_2 \neq 1$$

where  $\mu$  is the geometric mean titer.

P values and confidence intervals for the geometric mean titer ratio will be estimated using a generalized estimating equation linear regression accounting for site clustering.

*Endpoint iv:*

Geometric mean fold rise will be compared between group i (concomitant administration) and ii (influenza administered first), using the following null ( $H_0$ ) and alternative ( $H_1$ ) hypotheses:

$$H_0: \mu_1 / \mu_2 = 1$$

$$H_1: \mu_1 / \mu_2 \neq 1$$

where  $\mu$  is the geometric mean fold rise.

P values and confidence intervals for the geometric mean titer ratio will be estimated using a linear regression adjusted for site.

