## **APPENDIX 1**

### **Protocol Violations for Exclusions from Immunogenicity Analysis**

1. Missed visit/visit not conducted
2. Visit occurred outside of acceptable window
3. No pre- and/or post-vaccination blood draw or insufficient volume for assay analysis for respective vaccine
4. Did not meet inclusion
5. Met exclusion criteria
6. Delayed vaccine administration
7. Missed vaccine administration
8. Study product temperature excursion

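### SAP 9.2 carries the group i v group ii contrast over to SARS-CoV-2 vaccine response, where group iii is the comparator that EO2 needs

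*SAP*

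**What the plan says.** SAP section 9.1 writes the same pair of groups into all four HAI endpoints. For the GMT endpoint: "GMTs before and 28-42 days after immunization will be compared between group i (concomitant administration) and ii (influenza administered first"). SAP section 9.2, under Serology, then extends this: "Microneutralization (MN), SARS-CoV-2 binding antibody and viral neutralization, and circulating virus objectives will all use the same statistical methods as the primary HAI objective". Section 9 never mentions group iii.

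EO2 (SAP 2.2) concerns SARS-CoV-2 responses "against Moderna mRNA COVID-19 vaccine antigens following concomitant administration with cclIV4 or alone". Its endpoint (SAP 3.2) is the GMT "pre- and post-vaccination with mRNA COVID-19 vaccine". The second EO6 endpoint is the fold rise in "titers following mRNA COVID-19 vaccination (visit 1 to visits 2-3"), with no statement of which visit serves which group.

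On timing, Protocol 5.4.1, Table 1, places the COVID-19 dose at Visit 1 for groups i and iii and at Visit 2 for group ii. Protocol 5.1 says blood "will be collected prior to vaccination administration at Visit 1 (day 0) and Visit 2 (day 28"). SAP 6.4 requires MSD results at Visits 1 and 2, sets an analysis window of +14 days from target, and keeps only participants who "did not have an influenza or SARS-CoV-2 infection between visits 1 and 2".

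**The concern.** The HAI contrast works because groups i and ii both receive influenza vaccine on day 0 and differ only in whether COVID-19 vaccine was given with it. The mirror image for COVID-19 vaccine is group i v group iii: both receive COVID-19 vaccine on day 0 and differ only in whether influenza vaccine was given with it. Section 9.2 transfers the method without exchanging the arm.

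At stake is the reading of EO2 and the post-vaccination part of EO6, namely whether giving the influenza vaccine at the same time alters the COVID-19 vaccine response. With group ii as comparator, a difference could reflect the earlier influenza dose, the later calendar date or intercurrent infection instead. If no pair is specified, pair and visit can be settled after open-label data are in hand, with two-sided tests at 0.05.

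**Working it through.** **Step 1. Place each candidate sample.** Inputs: dose visits, the Visit 2 window of 28-42 days after Visit 1 and the draw-before-dose rule (Protocol 5.1 and Table 1); 28-42 days after immunization (SAP 9.1); the Visit 1-2 infection screen and the +14-day window (SAP 6.4). For group ii at Visit 3 the most favourable reading is used: target 28 days after Visit 2, plus 14, so 28-42 days post-dose.

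| Sample | Days since COVID-19 dose | Influenza vaccine relative to COVID-19 dose | Study day of sample | Post-dose interval covered by infection exclusion |
|---|---|---|---|---|
| Group i, Visit 2 | 28-42 | same day | 28-42 | all |
| Group iii, Visit 2 | 28-42 | not yet given | 28-42 | all |
| Group ii, Visit 2 | not yet dosed | already given | 28-42 | not applicable |
| Group ii, Visit 3 | 28-42 | 28-42 days earlier | 28+28 = 56 to 42+42 = 84 | none |

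**Step 2. Compare with group i at Visit 2.**
- Group iii at Visit 2 differs only in the day-0 influenza vaccine, which is the factor EO2 asks about. With no interference the expected GMT ratio is 1.
- Group ii at Visit 2 has no post-COVID-19-vaccine result.
- Group ii at Visit 3 matches on days since dose but differs in three ways: the dose follows influenza vaccination, it is given 28-42 days later, and infections after it are not excluded, because the Visit 1-2 screen ends where group ii's post-dose period begins.

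**Step 3. Cost in precision of changing the comparator.** The plan gives group sizes but no power calculation. Its sizes reproduce: 600 × (2/4, 1/4, 1/4) = 300/150/150 adults; 200 × the same = 100/50/50 children. Groups ii and iii are therefore equal.
- Adults, either pair: √(1/300 + 1/150) = 0.100.
- Children, either pair: √(1/100 + 1/50) = 0.173.

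With an assumed SD of log2 titre of 1.5 to 2.5 (not in the documents), the GMT ratio detectable with 80% power is 2^(2.80 × SD × 0.100) = 1.34 to 1.62 in adults and 2^(2.80 × SD × 0.173) = 1.66 to 2.32 in children. This is before exclusions, and applies where all samples are tested; the size of the neutralization subset is not stated. The figures are the same for i v ii and i v iii.

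**Step 4. Attrition from the window.** Protocol Visit 2 is already confined to 28-42 days, so i v iii loses nobody who attends within the protocol window. Protocol Visit 3 may fall 28-92 days after Visit 2, so holding group ii to 28-42 days drops later attenders. For an assumed loss of 25% or 50% of 150 adults (n = 112.5 or 75), the SE relative to the full groups is √(1/300 + 1/n)/0.100 = 1.11 or 1.29.

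**The case against.** **Timing can be matched.** The sentence in SAP 9.1 that names the pair also fixes 28-42 days after immunization. The +14-day window in SAP 6.4 is worded generally, and Appendix 1 item 2 excludes visits outside the acceptable window. Item 3 removes anyone with "No pre- and/or post-vaccination blood draw or insufficient volume for assay analysis for respective vaccine". Read together, these can hold group ii's Visit 3 sample to 28-42 days after its dose. This largely stands: time since dose need not be a source of bias. It does not remove the other three differences in Step 2.

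**A stronger reading that the documents do not support.** A reader might infer that waning alone would distort the i v ii ratio. Two figures illustrate this, assuming no true effect and a titre half-life of 60-120 days.
- If Visit 3 ran over its full 28-92 day window, mid-window timing would be day 60 v day 35 for group i at Visit 2. The i/ii ratio would be 2^(25/120) = 1.16 to 2^(25/60) = 1.33.
- If both groups were read at Visit 3, group i would be 28-42 days further from its dose. The ratio would be 2^(-42/60) = 0.62 to 2^(-28/120) = 0.85.

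The first requires that the +14-day window is not applied to Visit 3, which SAP 6.4 does not name. The second sets aside the 28-42 days in SAP 9.1. Neither is the natural reading. Likewise, running i v ii at Visit 2 would return the whole vaccine rise as the ratio (2 for an assumed twofold rise), but EO2's endpoint is post-vaccination, which argues against it.

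**Methods may mean models only.** This is possible, and SAP 6.4's anchoring on Visits 1 and 2 gives it some support. The comparator is then unstated rather than wrong. The protocol does not supply it: section 5.2.2.2 speaks of simultaneous v sequential groups, section 8.2 of vaccination groups, and section 8.2 leaves the exploratory analyses to the SAP. The same fix applies.

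**Alone could mean not at the same visit.** Protocol 5.2.2.2 includes both sequential groups, so a comparison with group ii is legitimate as a secondary question. Only group iii, however, has received COVID-19 vaccine without influenza vaccine when its post-dose blood is drawn.

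**Group iii will be reported anyway.** EO4 gives titres by visit for each group. That is a summary, not a named contrast.

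**Conclusion.** The point holds. Followed as written, SAP 9.2 uses the wrong comparator for EO2 and the post-vaccination part of EO6; read as models only, it leaves the contrast unspecified. Even with time since dose matched, group i v ii mixes the effect of concomitant influenza vaccine with prior influenza vaccination, a dose given 28-42 days later and infections that SAP 6.4 does not exclude. The documents give no basis for the size or direction of that mixture. Group i v iii at Visit 2 has none of these differences and fits the SAP 6.4 population as it stands.

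This conclusion rests on the schedule alone, not on any assumed SD, half-life or fold rise. It concerns exploratory endpoints only; the primary HAI analysis correctly uses group ii. It should be corrected before analysis but does not threaten the trial's main result.

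**What to change.** Amend SAP 9.2, Serology, to say:
- For SARS-CoV-2 vaccine response (EO2 and the post-vaccination part of EO6), the main contrast is group i v group iii with the section 9.1 models, Visit 1 to Visit 2, 28-42 days after the COVID-19 dose.
- Group ii's Visit 3 response, 28-42 days after its COVID-19 dose, is a secondary sequential comparison, reported with a 95% confidence interval and days since dose.
- Group i v ii is kept for the comparisons after influenza vaccination in EO1 and EO5.
- The other EO5 and EO6 visit and infection summaries by group stay as written.

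The cost is a short SAP edit. No visit, sample or assay is added, and planned group sizes and precision do not change. The downside is that the effect of giving influenza vaccine first on the later COVID-19 response becomes a secondary result.

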Study Duration:	12 months total Enrollment: Aug — Oct 2023 Vaccination: Aug — Nov 2023 Blood draws: Aug 2023 — May 2024 Active surveillance for illness: Aug 2023 — May 2024 Laboratory testing: Nov 2023 — Jul 2024
Participant Duration and Number of Participants:	
 • Up to 10 months (Aug 2023 — May 2024) • 800 total participants (600 aged 18-64 years, 200 aged 6-11 years) at 4 sites (only two sites will enroll children aged 6-11 years)
Randomization:	Adults aged 18-64 years, 2:1:1 permuted block randomization 
 i. Concomitant cclIV4 + COVID-19 mRNA (day 0) [n = 300] ii. Sequential cclIV4 (day 0), COVID-19 mRNA (day 28) [n = 150] iii. Sequential COVID-19 mRNA (day 0), cclIV4 (day 28) [n = 150]

	
Children aged 6-11 years, 2:1:1 permuted block randomization
 
 i. Concomitant ccIV4 + Moderna COVID-19 mRNA (day 0) [n = 100] ii. Sequential ccIV4 (day 0), Moderna COVID-19 mRNA (day 28) [n = 50] iii. Sequential Moderna COVID-19 mRNA (day 0), ccIV4 (day 28) [n = 50]

Description of Study Procedures:
	
This study is a randomized immunogenicity study in an enrolled cohort with active surveillance for acute respiratory illness (ARI). During this study, participants will be randomly assigned to receive an approved quadrivalent influenza vaccine (Flucelvax [ccIV4]) and mRNA COVID-19 vaccine (Moderna) either concomitantly (given in contralateral arms) or sequentially (28 days apart).
 
Blood samples from participants will be collected for measurement of biomarkers of immune response at baseline (visit 1; day 0), post-vaccination 1 (visit 2; day 28), post-vaccination 2 (visit 3; day 56), and post-season (visit 4; day 180). Serum and peripheral blood mononuclear cells (PBMC) and plasma (target to collect PBMC and plasma samples at every visit from a subset of approximately 250 participants; 200 adults and 50 children) samples will be isolated from whole blood and tested for biomarkers of vaccine immunogenicity, and duration of antibody responses.

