If a participant reports ARI symptoms at any point during the weekly electronic follow-up survey (ARI), they may be asked to complete an acute visit. These specimens may be drawn at the same time as scheduled visits 1-4.

- Obtain nasal/throat swab (**Section 5.5.4.3**)
- Obtain sera sample (**Section 5.5.4.1**), PBMC, and plasma sample (**Section 5.5.4.2**)
- Schedule convalescent visit 28 (28-42) days after acute visit for influenza or SARS-CoV-2 positive participants
- Confirm contact information and preferred method of contact for follow-up (telephone, text, or email)

Convalescent Visit, 28 (28-42) days after acute visit – Specimen Collection – Clinic Visit

If a participant tests positive for influenza and/or SARS-CoV-2 at any acute clinic visit, a convalescent visit is required 28 (28-42) days after their acute clinic visit. These specimens may be drawn at the same time as scheduled visits 1-4.

- Obtain sera sample (**Section 5.5.4.1**), PBMC, and plasma sample (**Section 5.5.4.2**)

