## 6.3 Influenza Immunogenicity Population

The Influenza Immunogenicity Population is a subset of the mITT Population that includes only subjects who received both vaccines, provide visit 1 and visit 2 blood draws available with HAI titer results for analysis within the protocol-defined time frame, did not have an influenza or SARS-CoV-2 infection between visits 1 and 2, and had no protocol violations affecting immunogenicity. Protocol violations affecting the immunogenicity analyses are defined in the Statistical Analysis Plan (SAP) Appendix 1. The acceptable visit window for sample analysis will be +14 days from the target date. Should 10% or more of the total study population be excluded from the Influenza Immunogenicity Population due to missing the visit window, then an additional analysis will be performed including these subjects with the missing visit window exclusion.

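### The waning analyses (EO3, EO4) run to about day 180 but exclude infection only between Visits 1 and 2, so titres raised by later infection bias the absolute decline rates, probably toward slower waning on net

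*SAP*

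**What the plan says.** **Endpoints.** SAP 3.2 sets EO3 as HAI and MN titres against vaccine and "circulating influenza virus antigens at visit 1, visit 2, visit 3, and visit 4 for each vaccination group". EO4 does the same for vaccine and "circulating SARS-CoV-2 virus antigens at visit 1, visit 2, visit 3, and visit 4 for each vaccination group". Each also has fold changes from Visit 1 to Visits 2, 3 and 4.

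**Follow-up.** Protocol 5.1 describes the last draw as "Visit 4 (day 180; end of local flu circulation". Table 1 puts it 152 (± 30) days after Visit 2. The Protocol Summary gives "Active surveillance for illness: Aug 2023 — May 2024".

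**Population.** SAP 9.2 states: "Serology and cell mediated immunity objectives will be analyzed using the immunogenicity population". In SAP 6.3 the infection criterion is that the participant "did not have an influenza or SARS-CoV-2 infection between visits 1 and 2", and SAP 6.4 uses the same words. None of the eight violations in SAP Appendix 1 is an infection. The immunogenicity population in Protocol 8.1 has no infection criterion either.

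**Model.** The waning sentence in SAP 9.2 names time since vaccination as the explanatory variable: "Waning objectives will use parametric models to estimate the rate of antibody decline by time since vaccination". It gives no infection term, censoring rule or sensitivity analysis. SAP 7.2 deals with missing values only. Protocol 8.2 leaves the detail of the exploratory analyses to the SAP, so no other text fills the gap.

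**Illness visits.** Protocol 5.4.1 says of acute and convalescent samples: "These specimens may be drawn at the same time as scheduled visits 1-4".

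**The concern.** The plan already accepts that infection contaminates a vaccine response, because it excludes infection in the first interval. It also expects infection to raise titres: EO5 and EO6 include the rise from acute to convalescent visit. Yet the exclusion stops at Visit 2, and the much longer stretch through the respiratory season is left open. A participant infected in that stretch stays in the model, with later titres read as antibody left over from vaccination. A Visit 3 or Visit 4 draw can even coincide with a convalescent visit, 28 to 42 days after the acute one.

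The window also fails to fit two combinations of arm and vaccine. Group iii receives the influenza vaccine at Visit 2, and group ii the mRNA vaccine. For those responses, Visits 1 to 2 lie wholly before the relevant vaccination. Their post-vaccination response is read at Visit 3, and infection between Visits 2 and 3 is not excluded.

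Duration of antibody response is in the study title. At stake are the published decline rates and half-lives, and the exploratory Visit 3 responses of the arms vaccinated at Visit 2.

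**Working it through.** The documents give no waning rate, attack rate or boost size, so there is no figure of the plan's own to reproduce. The check sets the exclusion against the interval being estimated, then illustrates direction and size.

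**1. Exclusion window against decline interval (Protocol Table 1; SAP 6.3, 6.4)**

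| Titres | Relevant vaccine | Decline interval | What the Visit 1–2 exclusion covers |
|---|---|---|---|
| Influenza, groups i and ii; SARS-CoV-2, groups i and iii | Day 0 | Visit 2 to 4, 180 − 28 = 152 days | Vaccination to first post-vaccination draw; none of the decline |
| Influenza, group iii; SARS-CoV-2, group ii | Day 28 | Visit 3 to 4, 180 − 56 = 124 days | Only time before the vaccine; neither the response nor the decline |

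**2. Size in an arm vaccinated on day 0, two-point version**

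Assume that a share x is infected after Visit 2 and that their Visit 4 titres remain k-fold above the uninfected course. The Visit 4 GMT is then multiplied by k^x, so

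- apparent fall = true fall / k^x
- half-life = 152 × ln 2 / ln(fall)

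Assumed true fall: 2.5-fold over 152 days, giving 152 × 0.693 / 0.916 = 115 days.

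- x = 5%, k = 4: fall 2.5 / 1.072 = 2.33, half-life 124 days
- x = 10%, k = 4: fall 2.5 / 1.149 = 2.18, half-life about 135 days
- x = 10%, k = 8: fall 2.5 / 1.231 = 2.03, half-life 149 days
- x = 20%, k = 8: fall 2.5 / 1.516 = 1.65, half-life 211 days (the extreme corner)

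**3. Direction, using a straight line in log2 titre**

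Assume a true fall of 1 log2 unit per 152 days, x = 10% and k = 4. The mean uplift is then 0.10 × 2 = 0.2 log2 units once every infection has shown.

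*Infections spread evenly over days 28 to 180, boost visible after 14 days and kept.* The share visible is 14/152 = 0.092 at Visit 3 and 138/152 = 0.908 at Visit 4, so the uplifts are 0.0184 and 0.1816.

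- Day-0 arm (days 28, 56, 180; mean 88; deviations −60, −32, 92; sum of squares 13,088): bias per 152 days = 152 × (−32 × 0.0184 + 92 × 0.1816) / 13,088 = +0.187. Decline is understated by about 19%.
- Day-28 arm (days 56 and 180): 152 × (0.1816 − 0.0184) / 124 = +0.20. Decline is understated by about 20%.

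*All infections between Visits 2 and 3 and visible at Visit 3.* Let s be the share of the log2 boost kept at Visit 4.

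- Day-28 arm: 152 × 0.2 × (s − 1) / 124 = 0 for s = 1, −0.123 for s = 0.5, −0.245 for s = 0. Decline is unbiased, or overstated by 12% or 25%.
- Day-0 arm: 152 × 0.2 × (−32 + 92s) / 13,088 = +0.139, +0.033 and −0.074 for the same values of s. This runs from 14% understated to 7% overstated.

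The sign therefore depends on when infections fall and how long the boost lasts. Infections spread across the season give slower apparent waning. Early infections with a transient boost can give the reverse, most clearly where Visit 3 is the first post-vaccination draw.

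**The case against.** **The estimand is partly a choice.** EO3 and EO4 do not say that waning is to be measured without infection. A curve through all titres legitimately describes antibody in vaccinees over a season. That stands, and it is why both curves should be reported. It does not rescue the current text, which excludes infection in one interval, ignores it in the next, and attributes the result to time since vaccination.

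**Every magnitude is assumed.** This also stands. The half-life formula uses two points, ignores Visit 3, and applies only to arms vaccinated on day 0. Its k is the elevation remaining at Visit 4, not the peak. Because EO3 is reported by antigen, one attack rate for all antigens is not justified.

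**Censoring has its own bias.** If participants with low or fast-falling titres are infected more often, removing their later titres also flatters persistence. Detection is incomplete as well, because swabbing is optional (Protocol 5.4.1 and 5.5.4.3). Both points are conceded.

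**The consequence is limited.** The objectives are exploratory. Randomisation is stratified by site and age group, so exposure should be broadly balanced between arms. A reader might infer that the randomised comparison of schedules is compromised. The documents do not support that: the primary analysis in SAP 9.1 compares groups i and ii at 28 to 42 days, inside the window where infection is excluded. Contrasts between arms in waning should also be less affected than the absolute rates.

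**Conclusion.** The point holds as a mismatch between the stated population rule and the interval being estimated. It is more than a missing detail: applying SAP 6.3, 6.4 and 9.2 as written keeps post-infection titres in the decline models. For group iii influenza titres and group ii SARS-CoV-2 titres, it excludes no post-vaccination infection from the response either.

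A reader might go further and conclude that waning will be understated in every arm. The documents do not settle this. Slower apparent waning is the likely net direction if infections are spread over the season, but step 3 of the working shows that the sign can reverse.

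Nor can the size be derived from the documents. The move from 115 to about 135 days rests on three assumptions: a 2.5-fold true fall, 10% infected, and a 4-fold residual boost. The omission is certain, the direction probable and the size unknown. The point is worth correcting before the exploratory serology is analysed, but it is no threat to the primary objective.

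**What to change.** **SAP 9.2, EO3 and EO4.** Pre-specify an analysis that censors a participant's titres against a virus from the earlier of two events after the relevant study vaccination:

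- the first documented infection with that virus (positive study swab, test result reported in the weekly survey, or medical-record test); or
- a non-study dose of that vaccine.

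Report the all-titres curve alongside, and say which question each curve answers. State that the completely-at-random assumption of SAP 7.2 is not carried over to censored titres.

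**SAP 6.3 and 6.4.** For exploratory responses, tie the infection exclusion to the pre/post interval of the relevant vaccine: Visits 1 to 2 when it is given at Visit 1, Visits 2 to 3 when it is given at Visit 2. The primary analysis does not change.

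A further analysis that drops titres after an unexplained four-fold rise is better left out, or labelled descriptive. It selects on the outcome and would remove upward assay error but not downward.

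**Cost.** SAP wording and one additional set of curves. The data are already collected: weekly surveys to Visit 4 (Protocol 5.5.2.2), acute-visit swabs (5.4.1), and vaccination and infection records to study end (5.7.1, 5.7.2). The downsides are fewer Visit 3 and 4 titres, undetected infections that remain in the model, and possibly informative censoring. Showing both curves keeps these limits visible.
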